4.4.1 Premature Termination of the Study and Stopping Criteria

The Sponsor will suspend or terminate a dose level or the entire study (as applicable) following the review of all available safety data if any of the following occurs at the dose or study level:

Per dose level (Part 1)

- Two participants experience a FEV₁ drop $\geq 30\%$ from baseline (in-clinic)* attributable to AZD1402.
- One participant experiences a hypersensitivity-like SAE attributable to AZD1402.

- Day 28 exposure in one participant in Part 1 exceeds or is predicted to exceed (for Part 1b) a peak concentration Cmax of 5420 ng/mL or exposure AUC(0-24 h) of 68700 ng.h/mL.

*Baseline Part 1: Mean of Day -1 and Day 1.

Per dose level (Part 2)

- Clinically significant FEV₁ decline from baseline* attributable to AZD1402 comparing the number of participants reaching a FEV₁ drop $\geq 30\%$ in active versus placebo as assessed by the DSMB.
- One participant experiences a hypersensitivity-like SAE attributable to AZD1402.

*Baseline Part 2: Mean of Day 1 (15 minutes and 45 minutes pre-dose).

Study level

- Two participants experience a hypersensitivity-like SAE and/or severe hypersensitivity event attributable to AZD1402.
- The overall safety and tolerability profile as determined by the DSMB does not justify continuation with dosing as per the current protocol.
- Significant immunogenicity impacting safety and tolerability.
- The Sponsor considers the applied doses of the study intervention to be no longer relevant.
- The Sponsor decides to discontinue the study.
- Data not known before, become available and raise concern about the safety of AZD1402 so that continuation would pose potential risks to the participants.

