- Last date of systemic corticosteroid dose.
- Date of discharge from emergency room or urgent care visit.
- Date of hospital discharge.
- If < 7 days have elapsed since the end date of an asthma exacerbation and the start date of a new asthma exacerbation, the second event will be considered a relapse of the prior asthma exacerbation in the statistical analysis.
- All asthma exacerbations that occur during the Treatment Period and Follow-up, must be recorded as an AE in the eCRF.

See Section [8.3.8](#) for additional information on recording asthma exacerbations as an AE/SAE during the study.

e-Diary Data and Exacerbations

Any sustained increase in asthma symptoms as reported via the e-Diary (or change in background medication that does not meet the definition of criteria of an asthma exacerbation) as defined in the protocol/study reference manual will be graded as a worsening of asthma and will include, but are not limited to:

- An increase in rescue medication use of 4 or more puffs on at least 2 consecutive days compared with the average use during the Run-in baseline or use of 12 puffs/day on any one day. Systemic steroid use for < 3 days (without hospitalisation \geq 24 hours).
Worsening of asthma should be recorded as AEs in the EDC.

Additionally alerts to the study site to inform AESIs/study stopping/suspension criteria and potential exacerbation/worsening of asthma will also be triggered as defined in the protocol/study reference manual. These may include, but are not limited to:

- FEV₁ decrease \geq 20% relative to the pre-dose assessment (Part 1 in-clinic assessment only), or
- FEV₁ decrease \geq 20% compared to baseline (Part 1 home assessment), or
- FEV₁ decrease \geq 20% compared to baseline (in-clinic assessment), or
- FEV₁ decrease \geq 30% on 2 consecutive scheduled time points compared to baseline (Part 2 home assessment), or
- Respiratory AESIs* (may include wheeze, cough, shortness of breath), or

- An increase in rescue medication use of 4 or more puffs on at least 2 consecutive days compared with the average use during the Run-in baseline or use of 12 puffs/day on any one day.

Participants will be required to keep a record of their asthma symptoms in the e-Diary as per the SoAs ([Table 1](#) and [Table 2](#)). The applicable data captured in the e-Diary will also be used to determine individuals **CCI** (Section [8.1.12](#)).

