8.3.4 Adverse Events Based on Signs and Symptoms

All AEs spontaneously reported by the participant or reported in response to the open question from the study site staff: 'Have you had any health problems since you were last asked?', or revealed by observation will be collected and recorded in the eCRF. When collecting AEs, the recording of diagnoses is preferred (when possible) to recording a list of signs and symptoms. However, if a diagnosis is known and there are other signs or symptoms that are not generally part of the diagnosis, the diagnosis and each sign or symptom will be recorded separately.

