All confidence intervals (CIs) will be 2-sided 95% CIs, unless stated otherwise, and presented to one more decimal place than the raw data recorded in the database. If a model is used to estimate the treatment difference, the corresponding CI according to the model will be presented. Otherwise, the unadjusted CI will be used. Nominal p-values may also be presented. Care should be taken when interpreting CIs and p-values since no correction for multiple testing is done for the endpoints.

P-values greater than or equal to 0.001, in general, will be presented to 3 decimal places. P-values less than 0.001 will be presented as “<0.001”.

Descriptive statistics for calculated PK parameters and FeNO will include: n , mean, SD, geometric mean, geometric coefficient of variation (GeoCV%), median, minimum and maximum values.

The GeoCV% will be calculated as $SQRT(es^2-1)*100$ where s is the SD of the log-transformed values.

Daylight saving dates will be considered in the calculation of the absolute scheduled and actual times and in the duration when this is based on times. Therefore, if any daylight saving change occurs during the study development, this will impact the description of the blood sample collections, the calculation of the PK parameters and any AE duration in case the time is included in the calculation of the duration.

Statistical Analysis Plan

All other requirements and specifications for programming and presentation of TFLs will be specified in the TFL shells document.

The following rules will be applied for any repeated safety assessments:

- For repeated assessments at any timepoint before first IP administration (including screening values and baseline): the latest assessment obtained per timepoint will be used in the calculation of descriptive statistics.
- For repeated assessments at any timepoint after first IP (including Follow-up visit): the first (non-missing) value after dosing will be used in the calculation descriptive statistics.

The AM and PM assessments will be combined into a daily assessment according to the following formula:

Let assessment (Day i) = (PM assessment (Day i) + AM assessment Day (i+1)) / 2

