- Any AE leading to discontinuation of IP
- Any AE leading to withdrawal from study

An overview summary of AEs together with a presentation of AEs (event count) by preferred terms and sorted by decreasing frequency on preferred term will be also produced. In addition, an overview summary of the number and percentage of subjects with AEs and by SOC, preferred term, and treatment will be also presented by ADA status.

Additional tables will present the number and percentage of subjects with any AESI occurring after first dose (including infection, eosinophilia, and hypersensitivity events) and the in-clinic alerts with the individual occurrences in those categories.

The AESI presented in the table will be (for in-clinic assessments):

- FEV₁ drop $\geq 20\%$ reduction from baseline as informed by in-clinic assessment: information extracted from the AE page on the eCRF.
- FEV₁ drop $\geq 30\%$ reduction from baseline as informed by:
 - in-clinic assessment.
 - decline is sustained over 2 scheduled consecutive home assessments resulting in either dosing suspension or discontinuation (Part 2).
- Confirmed fever ($> 38^{\circ}\text{C}$ for > 4 hours)
- Wheeze*
- Cough*
- Dyspnoea/shortness of breath*

Statistical Analysis Plan

- Infection
 - respiratory tract infection, ideally supported by pathogen identification and confirmation.
 - COVID-19 infection.
 - non-respiratory tract infection.

*Part 1: All new events of wheeze, cough, dyspnoea/shortness of breath.

Part 2: All new worsening events of wheeze, cough, dyspnoea/shortness of breath compared to baseline / individual pre-existing disease characteristics as judged by the Investigator.

In the event of suspected respiratory infection, pathogen identification include:

- SARS-CoV-2 PCR.
- Viral panel which may include but are not limited to influenza (all types), parainfluenza, respiratory syncytial virus, human metapneumovirus, adenovirus, and *Bordetella pertussis*.
- *Mycoplasma pneumonia* and *Chlamydophila pneumoniae* (sometimes included in viral panel).
- Bacterial swab to detect any growth which may include, but are not limited to *Streptococcus*, *Klebsiella*, *Pneumoniae*, *Pseudomonas*, *Staphylococcus aureus*, *E. Escherichia coli*, *Citrobacter*, *Acinetobacter* and *Haemophilus influenza*.

The number and percentage of subjects who experience one or more AEs will be tabulated by each study part, treatment group (dose level of AZD1402, pooled AZD1402, and placebo) and by:

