4.17.5 Spirometry

In-clinic and home spirometry values (FEV₁ and FVC) will be listed by subject and timepoint including absolute values, change from baseline, and percentage change from baseline.

Change from baseline will be calculated and presented by timepoint in each study part. Summary tabulations for absolute values, change from baseline and percentage change from baseline will be presented by treatment group (AZD1402, pooled AZD1402, and placebo) and overall, and by timepoint for in-clinic and e-Diary spirometry FEV₁. For in-clinic FVC similar tables will be presented.

For repeated post-baseline in-clinic spirometry morning measurements that are taken on the same day and time as a scheduled visit and timepoint, the best response value of the morning pre-dose will be used.

For repeated post-baseline home spirometry measurements that are taken on the same day and time as a scheduled visit and time point, the highest results of the morning pre-dose will be used.

For repeated follow-up post-baseline in-clinic spirometry morning measurements that are taken on the same day and time as a scheduled visit and time point, the best response value of the morning assessments will be used.

For repeated follow-up post-baseline home spirometry measurements that are taken on the same day and time as a scheduled visit and time point, the highest results of the morning assessments will be used.

For Part 1, tables and figures presenting FEV₁ by study day will be based on the morning pre-dose values in case not differently indicated.

For Part 1 and/or Part 2 the following figures will be presented:

- In-clinic FEV₁ absolute values (L), individual subject by study day/week.

Statistical Analysis Plan

- In-clinic FEV₁ percentage change from baseline, individual subject data by study day/week.
- FEV₁ home spirometry absolute values (L), individual subject data by study day.
- FEV₁ home spirometry percentage change from baseline, individual subject data by study day.
- In-clinic FEV₁ mean absolute values (L) by study day/week and treatment group.
- In-clinic FEV₁ mean percentage change from baseline by study day/week and treatment group.
- FEV₁ home spirometry mean absolute values (L) by study day and treatment group.
- FEV₁ home spirometry mean percentage change from baseline by study day and treatment group.

The summary statistics for FEV₁ in-clinic spirometry and e-Diary spirometry will be presented separately.

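### The SAP takes the in-clinic FEV1 fall ≥20% AESI from the AE page, names no source for the ≥30% row or the in-clinic alerts, and plans no by-arm count of threshold falls from the spirometry data

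*SAP*

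**What the plan says.** - **Definition.** Protocol 8.3.5 lists an in-clinic FEV1 reduction from baseline of ≥20%, and one of ≥30%, after first dose as AESIs. The ≥30% item also has a Part 2 home-spirometry leg. Under Protocol 8.1.1, in-clinic FEV1 is measured on equipment from a central vendor.
- **Source of the AESI table.** For the ≥20% row, SAP 4.17.1 specifies: "reduction from baseline as informed by in-clinic assessment: information extracted from the AE page on the eCRF". For the ≥30% row it repeats the kind of assessment but names no data source. The same tables are to show "the in-clinic alerts with the individual occurrences in those categories", again with no source or derivation.
- **Alerts.** Protocol 8.1.5: "Additionally alerts to the study site to inform AESIs/study stopping/suspension criteria and potential exacerbation/worsening of asthma will also be triggered". Its list of triggers includes an in-clinic fall of ≥20% from baseline, but the list is open-ended.
- **AE recording.** Protocol 8.3.4 says that "the recording of diagnoses is preferred (when possible) to recording a list of signs and symptoms".
- **Spirometry outputs.** SAP 4.17.5 plans listings, summaries of absolute value, change and percentage change, and individual and mean plots. It has no count of participants at or beyond a threshold. For repeated morning in-clinic readings at the same day and time as a scheduled timepoint, "the best response value of the morning pre-dose will be used".
- **General repeat rule.** For repeated safety assessments after first dose, SAP 4.2 says "the first (non-missing) value after dosing will be used in the calculation descriptive statistics".
- **Use of the ≥30% count.** The Part 2 dose-level criterion in Protocol 4.4.1 concerns a clinically significant decline "attributable to AZD1402 comparing the number of participants reaching a" fall of at least 30% on active and placebo, as judged by the DSMB.

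**The concern.** The event is a number read from a spirometer, but the only stated source for the ≥20% row is an investigator's entry. A participant is counted only if the site notices the crossing, enters it, and enters it in a form that maps to that row. Given the general preference for diagnoses, a fall during an exacerbation or infection could be entered under the diagnosis alone. An infection would still appear in the AESI table, but under another row; an exacerbation is not an AESI category. SAP 4.17.1 also says that AEs unresolved at the last assessment are listed but left out of the AE summary tables. Read literally, that could remove a persisting fall from an AE-sourced count.

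FEV1 decline matters here. Protocol 2.3.1 names it, with respiratory events, among the observations that changed the known risk profile, and it enters the stopping criteria. The SAP plans threshold counts for haematology limits and hsCRP change (4.17.2), vital signs (4.17.3) and QT/QTc (4.17.4), but none from measured FEV1.

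**Working it through.** The plan states no expected rate of falls and no rate of entry on the AE page, so there is no figure to reproduce. The check is a comparison of sources, followed by two illustrations on assumed inputs.

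**1. What is counted, and from what**

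| Quantity | Defined by | Source named in SAP | Count by arm planned |
|---|---|---|---|
| In-clinic fall ≥20% (AESI) | measured value | AE page | yes, from AE page |
| Fall ≥30% (AESI) | measured value | none | yes, source unknown |
| In-clinic alerts | thresholds in Protocol 8.1.5 (open list) | none | yes, derivation unknown |
| Spirometry data (SAP 4.17.5) | measured value | spirometry | means and plots only |

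No line compares the AE-page count with the measured values.

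**2. Incomplete entry.** Expected count = n × p × c, with n = 80 per main arm (SAP 3.1.2), p = true proportion with a fall (assumed 5% to 15%) and c = share entered under the right term (assumed 70% to 100%).

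| p | c = 100% | c = 80% | c = 70% |
|---|---|---|---|
| 5% | 4.0 | 3.2 | 2.8 |
| 10% | 8.0 | 6.4 | 5.6 |
| 15% | 12.0 | 9.6 | 8.4 |

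For 15% against 5%, the difference is 12.0 − 4.0 = 8.0 participants at full entry and 8.4 − 2.8 = 5.6 at 70%. With equal capture in both arms the ratio stays at 3; the absolute excess shrinks. At c = 100% nothing is lost.

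**3. Repeat rule, if it were carried into a new threshold count.** Let t be the true fall, T the threshold and s the within-session SD in percentage points of change (assumed 2 to 6), with independent normal errors. The first reading crosses with probability p₁ = Φ((t − T)/s). The better of two crosses only if both do, with probability p₁².

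- t = T: 0.50 on the first reading, 0.50² = 0.25 on the better of two.
- t = T + 3: 0.93 against 0.87 (s = 2); 0.69 against 0.48 (s = 6).
- t = T + 6: 0.999 against 0.997 (s = 2); 0.84 against 0.71 (s = 6).

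The loss is concentrated in repeated readings near the threshold. For example, with an assumed baseline of 2.00 L, a reading of 1.58 L is 1.58/2.00 − 1 = −21%. A same-time repeat of 1.70 L is −15%, and under the best-value rule only the repeat is summarised.

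**4. The opposite error.** Counting any reading that crosses gives 1 − (1 − p₁)². For a true fall 3 points short of the threshold and s = 4, p₁ = 0.227. The any-reading probability is 1 − 0.773² = 0.40, against 0.05 for the better of two. A count from all readings will include some falls that are only measurement error.

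**5. Baseline.** For Part 2 in-clinic FEV1, SAP 4.6.1 gives the mean of the two Day 1 pre-dose values in one bullet and the Visit 1 pre-bronchodilator value in another. SAP 4.17 gives the last value before first dose for safety. Protocol 4.4.1 and 7.1.1 use the Day 1 mean. A threshold count must name one.

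**The case against.** The strongest case is that little is likely to be lost.

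- Protocol 8.3.5 is specific: the measured fall itself qualifies, and for the 20% item it supplies the reporting term. The general preference for diagnoses in 8.3.4 need not override that.
- Such a fall is also on the alert list, and alerts are to be tabulated. If the alerts are generated from spirometry, the SAP may already contain something close to the missing count.
- All FEV1 values, including unscheduled ones, are listed with percentage change, and individual plots are planned.
- An in-clinic fall of ≥30% leads to permanent discontinuation of dosing under Protocol 7.1.1, so it should also show among treatment discontinuations.

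Much of this stands. It rules out saying that falls will be undercounted or that the data are hidden. It does not close the gap: the alert derivation is not stated, listings and individual plots give no count by arm, and nothing reconciles the sources.

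A reader might infer four stronger things that the documents do not support:

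- **Both thresholds come from the AE page.** That source is written only for ≥20%; for ≥30% it is unstated.
- **The DSMB stopping rule is compromised.** The DSMB reviews unblinded data under its own charter, which is not among the documents, and does not depend on this table.
- **The best-value rule lowers the AESI count.** It governs the spirometry summaries, covers only morning repeats at the same day and time as a scheduled timepoint, and does not feed AE-page entries.
- **Best should be replaced by first.** SAP 4.17.5 is specific to spirometry, and Protocol 8.1.1 refers to a best-test process in a manual outside the documents. Keeping the best value for mean summaries is defensible.

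**Conclusion.** The point holds as a gap in source and cross-check. For an AESI defined by measurement, the ≥20% count relies on AE entry, the ≥30% row and the alerts have no stated source, and no by-arm count is derived from spirometry already held. Incomplete entry can only omit measured falls, so the supportable statement is that falls could be missed. How many, or whether any, cannot be derived from the documents. The 70% to 100% capture and 5% to 15% rates above are assumptions that show scale only, and at full capture the loss is zero. The repeat-rule figures rest on assumed normal, independent errors with an SD of 2 to 6 points. They bear only on how a new count should be built. This is a low-cost improvement to the safety reporting and does not bear on the primary efficacy analysis.

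**What to change.** In SAP 4.17.5, add one table by arm and part giving the number and percentage of participants with any post-baseline in-clinic FEV1 at least 20%, and at least 30%, below baseline.

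- Derive it from the spirometry dataset, using scheduled, repeat and unscheduled readings.
- Use the protocol baseline: for Part 1 the mean of Day −1 and Day 1, for Part 2 the mean of the two Day 1 pre-dose values. State that this governs over the other baselines in SAP 4.6.1 and 4.17 for this table.
- Show the AE-page AESI count beside it and list participants who appear in one source only.
- In SAP 4.17.1, state the data source for the ≥30% row and the derivation of the in-clinic alerts.
- Keep the best-value rule for the mean summaries. State that it overrides the general first-value rule in SAP 4.2 for spirometry, and that it does not apply to the threshold count.

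The cost is one derived table, one mismatch listing and a few sentences; no new data are needed. The downside is that some isolated poor-effort readings will be counted. A footnote should say so and identify crossings not reproduced on a same-time repeat.

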8.3.1 Time Period and Frequency for Collecting AE and SAE Information

Adverse events will be collected from time of signature of the ICF throughout the Treatment Period and including the Follow-up Period.

Serious AEs will be recorded from the time of signing of the ICF.

If the Investigator becomes aware of an SAE with a suspected causal relationship to the study intervention that occurs after the end of the clinical study in a participant treated by him or her, the Investigator shall, without undue delay, report the SAE to the Sponsor.

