9.4.3.1 Adverse Events

Adverse events will be coded using the most recent version of the MedDRA.

Adverse events will be presented separate for each Part by treatment, SOC and/or PT presenting number and percentage of participants reporting at least one event. Number of events will be presented separately.

Only AEs occurring with an onset date, or worsening, on or after first dose of study intervention will be presented in summary tables. Adverse events occurring prior the first dose of study intervention will be included in data listings.

An overview of AEs will be presented for each Part and treatment. The presentation will include the number and percentage of participants with any AE, AEs with outcome of death, SAEs, AEs leading to discontinuation of study intervention, AEs leading to withdrawal from study, and AEs of special interest (including infection, eosinophilia, and hypersensitivity events) as well as the number of individual occurrences in those categories.

An additional table will present the number and percentage of participants with most common AEs. Most common (eg, frequency of >5%) will be defined in the SAP.

In accordance with the requirements of the FDA, a separate table will present non-serious AEs occurring in more than 5% of participants in any treatment group.

Key participant information will be presented for participants with SAEs with outcome of death, SAEs, and AEs leading to discontinuation of study intervention.

An AE listing for the SS will cover details for each individual AE; an AE listing for participants who were not exposed to study intervention will be presented separately.

Full details of the AE analyses will be provided in the SAP.

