4.17.1 Adverse Events/Serious Adverse Events

Adverse events will be coded using MedDRA latest available version.

All reported AEs will be listed along with the date of onset, date of resolution (if AE is resolved), investigator's assessment of intensity, outcome, action taken with IP, and possible relationship to study drug (assessed by investigator). A by subject listing of all AE (including AEs before first dose of study medication) will be provided. This listing will include the following information: study period, verbatim term, MedDRA SOC, and preferred term, start date/time, end date/time, time from last dose, intensity, causality, action taken, whether the AE was classified as serious, the outcome of the AE and the concomitant or additional treatment given, if any. Any AE occurring before the first dose of IP and/or the AE assessments that are unresolved at the participant's last assessment in the study will be included in the data listings but will not be included in the summary tables of AEs.

Multiple occurrences of an AE in the same subject will only be counted once overall considering start date as the first day of first occurrence and stop date the last day of the last occurrence and the AE will assigned to the treatment of the first occurrence period study drug. Multiple occurrences of an AE in the same subject for the same treatment will only be counted once for that treatment.

Statistical Analysis Plan

The number of subjects will be tabulated also by SOC, preferred term, and treatment.

In the case that, during the study, a subject has more than 1 episode of the same preferred term with different levels of intensity, action taken, outcome causality or seriousness, then the maximum intensity level, action taken (ie, withdrawn) and outcome (ie, fatal), causality level (ie, related), or seriousness level (ie, serious), respectively will be used.

The following ordering will be used to define maximum intensity level, action taken, outcome causality level, or seriousness level:

- Intensity: Mild < Moderate < Severe
- Causality: No < Yes
- Seriousness: No < Yes
- Action taken: Unknown < Not applicable < Dose not changed < Drug interrupted < Drug withdrawn
- Outcome: Unknown < Recovered/resolved < Recovered/resolved with sequelae < Recovering/ resolving < Not recovered/not resolved < Fatal

A general summary of all AEs will show the number and percentage of subjects with:

- Any AE
- Any SAE
- Any SAE with outcome death

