- SOC and preferred term.
- SOC, preferred term, and maximum intensity.
- SOC, preferred term, and relationship to study intervention judged by investigator.

Adverse event summaries will be ordered in terms of decreasing frequency for SOC, and preferred term within SOC.

The tables of AE will include all the AEs with an onset date and time on or after the date and time of first dose of IP up to the end of treatment + 96 hours. Additional tables including all the AEs experienced after the IP until last follow-up (Day 56) and for ADA status will be reported for both Part 1 and Part 2.

Adverse events sorted by decreasing frequency and AEs leading to discontinuation of investigational product by SOC and preferred term will be summarised.

The number and percentage of subjects who experience 1 or more SAEs will be tabulated by treatment group (AZD1402 and placebo) and by SOC and preferred term and by SOC and preferred term and with outcome of death.

For each subject and each AE, the worst severity recorded will be attributed and used in the by-severity summaries. Similarly, the worst causality (most related to treatment) will be attributed and used in the by-causality summaries. If severity or causality is missing, a conservative approach for AE assessment (taking into account the worst case) will be followed.

Key subject information for participants experiencing SAE with outcome death, SAEs, and AEs leading to discontinuation of IP will be presented in a listing. All the AE will be included in the data listings.

Statistical Analysis Plan

For AEs with partial dates/times, worst case is always assumed; if possibly on-treatment, then on-treatment is assumed, on-treatment AEs will be considered to have the longest possible duration and off-treatment AEs will be considered to have the shortest possible duration. In accordance with this principle, any AEs with incomplete start and end dates/times will be treated as follows:

- AEs with unknown start times, but with start date known, will be imputed with a time of 00:00, unless the start date corresponds to any given dosing date. In this case the start time will be imputed with the time of dosing. If this results in a start date/time after end date/time of the AE, then the time will also be imputed with 00:00.

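### The SAP tabulates AEs by onset only, while the protocol also tabulates worsening after first dose, so a pre-dose AE that worsens on treatment can be left out of the general AE tables

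*SAP*

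**What the plan says.** **Protocol rule.** Section 9.4.3.1: "Only AEs occurring with an onset date, or worsening, on or after first dose of study intervention will be presented in summary tables". Events before first dose go to listings.

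**SAP rule.** Section 4.17.1: "The tables of AE will include all the AEs with an onset date and time on or after the date and time of first dose", with the window closing 96 hours after the end of treatment. Worsening is not mentioned. The same section takes "Any AE occurring before the first dose of IP" and says that such events "will be included in the data listings but will not be included in the summary tables of AEs", with no exception for an event that later gets worse. A further set of tables extends the window to Day 56, again without a worsening rule.

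**AESI tables.** SAP 4.17.1 adds: "Additional tables will present the number and percentage of subjects with any AESI occurring after first dose". For Part 2 the respiratory symptoms counted there are "All new worsening events of wheeze, cough, dyspnoea/shortness of breath compared to baseline / individual pre-existing disease characteristics as judged by the Investigator". For Part 1 only new events of these symptoms are counted.

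**Collection.** Protocol 8.3.1: "Adverse events will be collected from time of signature of the ICF throughout the Treatment Period". SAP 3.2.2.1 agrees. The AE footnote to the SAP's Part 2 schedule (Table 3) does not: it starts non-serious AEs at randomisation. Protocol 8.3.2 and SAP 3.2.2.1 list one start, one stop and one maximum intensity per AE. For SAEs the date on which seriousness was reached is also collected. No date of change in intensity is listed.

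**Declared changes.** SAP 4.20 names the removal of some exploratory endpoints, the per-protocol analysis and the subgroup analysis. The revision history adds the extra AE tables, the ADA-status tables and the hsCRP outputs. Neither mentions dropping the worsening criterion.

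**The concern.** The SAP is the document that will be programmed. If it is followed as written, an event that the protocol requires in the summary tables may appear only in a listing, and listings give no counts by arm.

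The kind of event matters here. Protocol 2.3.1 reports respiratory signs and symptoms, sometimes with a fall in FEV₁, in an earlier AZD1402 study. Participants have asthma and pass through screening and run-in, with AEs collected from consent, before first dose. A symptom that is mild before dosing and becomes worse on drug is one form that a drug effect could take. An onset-only rule treats it in the same way as a run-in symptom that never changed. Safety and tolerability are the primary objective of Part 1 and a secondary objective of Part 2.

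**Working it through.** The documents give no figure to reproduce, so the check is a comparison of the two rules on the possible kinds of record.

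| AE record | Protocol 9.4.3.1 | SAP 4.17.1 general AE tables |
|---|---|---|
| A. Starts on or after first dose | in | in |
| B. Starts before first dose, does not worsen | out | out |
| C. Starts before; worsening entered as a new AE dated after first dose | in | in, unless merged with the earlier record |
| D. Starts before; worsens after first dose; kept as one record | in | out |

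**Row D** is the conflict. The record has a pre-dose start, so the inclusion sentence does not admit it and the exclusion sentence sends it to listings. The intensity data cannot rescue it, because one maximum per record does not show whether the maximum came before or after first dose. A change to serious can be dated, but the SAP rule does not use that date.

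**Row C** is not fully safe either. SAP 4.17.1 counts repeated occurrences of an AE in one participant once overall and dates them from the first occurrence. If that merging is done before the onset filter, the post-dose record takes the run-in start date and becomes a row D record. The SAP does not give the order of the two steps.

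**Which tables.** The rule governs the tables by SOC and preferred term, by maximum intensity and by causality, and the SAE and discontinuation tables.

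**What the AESI tables recover.** In Part 2, worsening wheeze, cough and dyspnoea is counted there. In Part 1, worsening of a symptom that was already present is not named. Events outside the AESI list are not recovered in either part.

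**Weight of one participant** (planned numbers from Protocol 4.1.1 and 4.1.2):
- Part 1a: 30 randomised 1:1:1, so 30/3 = 10 per arm; 1/10 = 10 percentage points.
- Part 1b: 15 randomised 2:1, so 10 active and 5 placebo; 1/10 = 10 points and 1/5 = 20 points.
- Part 2, the two main arms: 80 planned per arm; 1/80 = 1.25 points. This SAP version anticipates closure, so the actual arms may be smaller.

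**Number affected.** This would need the proportion of participants with an AE open at first dose, the proportion of those that worsen, and the proportion kept as a single record. The documents give none of the three.

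**The case against.** A reader might infer that run-in respiratory events that worsen on drug disappear from the safety summaries altogether. The documents do not support that, for four reasons.

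1. **The AESI tables count the main Part 2 symptoms.** Falls in FEV₁ of 20% and 30% are also tabulated there, and FEV₁ is summarised by timepoint and treatment (SAP 4.17.5). This stands for Part 2. It does not cover worsening of existing symptoms in Part 1 or events outside the AESI list, and it does not put the event into the SOC/preferred term, intensity or causality tables.
2. **Worsening may be a new record.** Protocol Appendix B 1 lets a deterioration be an AE. Sections 8.1.5 and 8.3.8 ask for worsening of asthma to be recorded as an AE. Such a record would have a post-dose onset. This stands as a possibility: neither document says that worsening stays in one record, and neither requires a new record when a run-in AE is still open. The CRF completion instructions are not available to settle it.
3. **The pool is limited.** Under Protocol 8.3.8, symptoms in keeping with baseline asthma are not AEs unless they qualify as AESIs. Clinically significant respiratory infection, systemic corticosteroids or sustained heavy SABA use during run-in exclude a participant. Part 1 participants must be controlled at randomisation. If the SAP Table 3 footnote were followed, non-serious Part 2 AEs before randomisation would not be recorded at all. This stands as a reason to expect few cases. It does not remove mild events, or AEs of other kinds, that are open at first dose.
4. **Nothing is lost from the listings.** All AEs are listed, and key information is listed for deaths, SAEs and discontinuations. That is true, but it gives no comparison between arms.

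A reader might also attach a count per arm to the loss. Any such count would rest on invented rates.

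**Conclusion.** The two documents state different rules for which AEs are tabulated, and the SAP does not declare the difference. If the SAP is programmed as written, an AE that began before first dose, is kept as one record and worsens on treatment is left out of general AE tables in which the protocol requires it.

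The effect is narrower than a loss of respiratory safety data. It falls mainly on Part 1 symptoms and on non-AESI events. Its size cannot be derived; each omitted participant is worth 10 percentage points in a Part 1 active arm and 1.25 points in a main Part 2 arm at planned size. The conclusion assumes that the SAP sentences are applied literally and that at least some events are held as single records. It should be corrected before database lock, because the correction is cheap and the present rule can only undercount relative to the protocol.

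**What to change.** 1. In SAP 4.17.1, extend the inclusion rule to AEs with worsening in intensity or seriousness on or after first dose, within the windows already stated, and make the same exception in the sentence that sends pre-dose AEs to listings.
2. State that occurrences are not merged across first dose, so that a post-dose record does not inherit a run-in start date.
3. Before lock, query AEs that started before first dose and were still open after it, to date any worsening. For worsening to serious, the date already collected can be used.
4. Reconcile the start of AE collection in the SAP Table 3 footnote with Protocol 8.3.1 and SAP 3.2.2.1.

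If the sponsor prefers the onset-only rule, it should be declared and justified in SAP 4.20.

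Cost: a few SAP sentences, a small programming change and a limited query. AE counts would be slightly higher in all arms. An instruction to sites to open new records would come late for data already collected, so the query is the practical route.
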